9.4 Safety Analyses

- We shall continuously monitor and document all serious adverse events (SAEs), categorizing them by severity, causality, and timing relative to the intervention. This includes both anticipated events related to cancer and potential unexpected events related to the intervention.

- Comparative Analysis: Compare the incidence rates of SAEs between the intervention and control groups. This can help ascertain whether the intervention group experiences a higher rate of events, indicating potential safety concerns.
- The Trial Monitoring Committee shall regularly monitor these and can decide to forfeit the trials when there are clear indications that safety of the survivor is in danger due to our intervention
- Along with that we shall utilize QoL and well-being measures to indirectly assess safety, as significant declines could indicate adverse impacts of the intervention.

9.5 Other Analyses

- Futility Analysis: will be accessed to the inability of the clinical trial to achieve the primary and secondary objectives. In that case, both operational and statistical futility will be analyzed. Operational futility includes slow recruitment or slow accumulation of primary endpoints. Statistical futility includes, for the most part, group sequential methods and conditional power.

9.6 Interim Analyses

- Interim analyses are planned to evaluate the primary and secondary objectives' safety and efficacy data. These analyses may also explore data trends that could necessitate adjustments to the trial conduct.
- Statistical Methods:
 - The interim analyses will employ group sequential testing methods with an O'Brien-Fleming spending function to rigorously control the type I error rate across multiple looks at the data.
- Execution:
 - The analyses will be performed by an independent biostatistician from the trial investigators to maintain objectivity.
- Timing and Triggers
 - Scheduled Interim Analyses: Interim analyses are planned at 3 months, 6 months and 12 months of trial commencement.

- Ad Hoc Requests: Additional interim analyses may be conducted at the request of the Trial Monitoring Committee, particularly if unexpected safety concerns arise.
- Decision Criteria and Oversight
 - Decision Criteria: The criteria for early stopping or trial adaptation include a pre-specified boundary for efficacy (significant improvement in Quality of Life Scores or improvement in health outcomes) or safety concerns (unacceptable adverse events rate).
 - The Trial Monitoring Committee will oversee the interim analyses, reviewing the results to make recommendations on continuing, stopping, or modifying the trial.
 - Blinding Integrity: Individuals analyzing the data may have access to unblinded data; however, measures will be taken to ensure that the trial team remains blinded to maintain the integrity of the trial implementation.
 - Authority to Stop or Modify: The ultimate authority to stop or modify the trial rests with the TMC, in consultation with the principal investigator and the sponsor, based on the interim findings and established stopping guidelines.

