1.2 Trial Schema

1.3 Schedule of Activities

- Step 1: Enrollment and Intervention
 - Screening (including baseline assessment)

- Randomization by recruitment to test or control groups
- Informed Consent
- Access to control and test programs
- Regular Assessments up to 18 months
- Step 2: Data Analysis
 - Interim Data analysis will be 3 months, 6 months, 12 months and 18 months data.
- Step 3: Publication
 - Publication on protocol analysis and outcomes data is expected at 12 months and the end of 18 months

Section 2: INTRODUCTION

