4.4 Start of Trial and End of Trial

- Start of Trial: Defined by the first participant's enrollment (FPI).
- End of Trial: Marked by the last scheduled follow-up of the final participant, with an anticipated end date eighteen months post final participant enrollment to allow comprehensive long-term outcome analysis.
- Early Termination: Criteria for early trial termination will include lack of efficacy, safety concerns, or regulatory guidance, detailed in Section 10.5 with responsibilities clearly outlined for both sponsor and investigator.

Section 5: TRIAL POPULATION

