6.1 Schedule of Events

Schedule of events for test/treatment group:

Intervention or Assessment (Test)	Baseline (Day -30 to -1)	Week	Week	Month 1-6 (Every 30 days)	Month 7-18 (Every 30 days)
		1/3/5/7/9/11/13/15/17/19/21/23/...	2/4/6/8/10/12/14/16/18/20/22/24/...		
Live Coactive Lifestyle Coaching		X	X		

- 3-5 days per week, 45 mins each					
Async access to Lifestyle modification content curated by CT		X	X		
Informed Consent	X				
Eligibility Criteria Assessment	X				
Demographic Details	X				
EHR Access Consent	X				
Claims Data Access	X		X		X
QoLS (FACT-G Form)	X		X		X
Weight	X		X		X
Motivation to work	X	X			X
Employee Performance Review	X	X			X
Absenteeism Questions	X	X			X
Claim data validation with				X	X

survivor						
Cancer Progression Status					X	X

Schedule of events for active comparator (control) group:

Intervention or Assessment (Test)	Baseline (Day -30 to -1)	Week	Week	Month 1-6 (Every 30 days)	Month 7-18 (Every 30 days)
		1/3/5/7/9/11/13/15/17/19/21/23/... /47	2/4/6/8/10/12/14/16/18/20/22/24/... /48		
Async access to publically available lifestyle modification guidance		X	X		
Informed Consent	X				
Eligibility Criteria Assessment	X				
Demographic Details	X				
EHR Access Consent	X		X		X
Claims Data Access	X		X		X
QoLS (FACT-G Form)	X		X		X
Weight	X		X		X
Motivation to work	X	X			X
Employee Performance Review	X	X			X
Absenteeism Questions	X	X			X
Claim data validation with survivor				X	X
Cancer Progression Status				X	X

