8.4 Adverse Events and Serious Adverse Events

A serious adverse event (SAE) in this trial is defined according to the following severity grades:

- Grade 1: Mild discomfort, not interrupting normal activities
- Grade 2: Moderate discomfort, interrupts normal activities but not incapacitating
- Grade 3: Severe, resulting in disability or necessitating medical consultation (SAE)
- Grade 4: Requires hospitalization (SAE)
- Grade 5: Results in death (SAE)

Only events classified as Grade 3, 4, or 5 are considered SAEs within the context of this trial

- Time Period and Frequency for Collecting SAE Information
 - Time period
 - Start: Apr 15, 2024
 - End: Oct 15, 2025
 - Frequency
 - SAEs will be documented as they are reported by participants.
- Recording of SAEs
 - While prior studies suggest minimal evidence of SAEs resulting from exercise, diet, or meditation in cancer survivors, all SAEs encountered during this trial will be meticulously recorded. Participants can report SAEs directly via the app, or coaches may report on their behalf. Reports should include the severity grade, description of the event, and the participant's perspective on whether the SAE was related to trial interventions.
- Follow up of SAEs

- All participants will continue receiving standard care from their healthcare providers. In the event of an SAE, a dedicated physician will be assigned to assess the situation, provide immediate recommendations, and categorize the cause of the SAE based on discussions with the participant. This classification will also be documented.
- Regulatory Reporting Requirements for SAEs
 - SAEs must be reported to the Institutional Review Board (IRB) within 24 hours of the event's identification. Additionally, the Sponsor will ensure prompt notification of all investigators regarding any SAEs, enabling them to inform participants about potential risks and take any necessary precautions.
- The grading of adverse events is aligned with the Common Toxicity Criteria for Adverse Events (CTCAE) standards, which detail adverse events on a scale from 1 to 5. The complete CTCAE documentation is available on the National Cancer Institute's website: [NCI CTCAE Information](#).

Section 9: STATISTICAL CONSIDERATIONS

The analysis will be conducted on all participant data at the end of 3 months, 6 months, 12 months and 18 months (ie. end of the trial).

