9.2 Analyses Supporting Primary Objective(s)

The primary analysis will focus on quantifying the impact of **Complement Theory on changes in Quality of Life Score (QoLS), measured by the FACT-G instrument**, over the trial period. Assessments will occur at baseline, 3, 6, 9, 12, and 18 months.

- **Statistical Model, Hypothesis, and Method of Analysis**

- Primary Estimand (Change in QoLS):
 - Null Hypothesis (H0): There is no difference in the mean change in FACT-G QoLS between participants in the Complement Theory program and those in the control group at specified time points.
 - Alternative Hypothesis (H1): Participants in the Complement Theory program demonstrate a statistically significant improvement in QoLS compared to the control group.
- Baseline Data Analysis: Baseline demographics and characteristics will be provided and summarized in both treatment and control groups. Standardized mean differences (SMDs) will be calculated as the measure of distance between groups. SMDs of 0.2 to <0.5, 0.5 to <0.8 and ≥0.8 are considered small, medium, and large, respectively. Frequencies and percentage will be provided for the binary variables as well as the categorical variables (Yes/No); mean (standard deviation) and median (range) will be computed for continuous variables.
- Method of Analysis: Mixed models for repeated measures (MMRM) will be utilized to analyze changes in FACT-G scores over time, accounting for within-subject correlations. This model allows for the inclusion of both fixed effects and random effects to account for individual variability. In addition, covariate-time interaction terms will be included to guarantee the best results. The strength of the effect from each covariate will be evaluated

through the statistical test significance, i.e., P value, at 95% confidence interval.

- **Handling of Intercurrent Events of Primary Estimand(s)**

- For participants who discontinue the intervention or are non-adherent, we will employ a treatment policy strategy. This means all data collected will be analyzed as per the initial treatment assignment, regardless of the discontinuation or level of adherence, preserving the intention-to-treat principle.

- **Handling of Missing Data**

- Given the potential for missing QoLS data due to dropout or non-response, a multiple imputation (MI) approach will be adopted. The imputation model will incorporate variables predictive of missingness and outcomes to generate plausible values for missing data.

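### The efficacy looks have two incompatible timing rules, and neither a FACT-G visit nor an information fraction is named for the stopping boundary

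*Protocol*

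**What the plan says.** Protocol Section 9.6: "Interim analyses are planned at 3 months, 6 months and 12 months of trial commencement". Section 4.4 gives the origin of that clock: "Start of Trial: Defined by the first participant's enrollment (FPI". Read together, the looks fall on calendar dates counted from the first enrolment.

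Two other places describe the timing differently. Section 1.3: "Interim Data analysis will be 3 months, 6 months, 12 months and 18 months data". The opening sentence of Section 9: "The analysis will be conducted on all participant data at the end of 3 months, 6 months, 12 months and 18 months". Both can be read as follow-up time, with each look waiting until participants have reached the stated month.

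The end of the trial is also described in two ways. Section 4.4 has an "anticipated end date eighteen months post final participant enrollment". Section 9 lists analyses "at the end of 3 months, 6 months, 12 months and 18 months (ie. end of the trial".

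On FACT-G timing, Section 9.2 says "Assessments will occur at baseline, 3, 6, 9, 12, and 18 months". The Schedule of Events (6.1) marks the row "QoLS (FACT-G Form" at baseline, in the even-week column and in the column for months 7 to 18, which is far more often.

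Section 9.6 specifies an O'Brien-Fleming spending function and allows early stopping on an efficacy boundary for quality of life. It gives no information fractions. Section 9.2 refers to specified time points without naming a primary one.

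Sections 1.3, 4.4, 9 and 9.6 of the combined protocol and SAP carry the same timing wording, with healthcare expenditure as the primary outcome.

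**The concern.** A spending function converts the share of information available at a look into the share of alpha that may be used. To apply it, one must know what counts as information and when the look takes place. Here the clock has two readings and the visit is not named.

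The clock matters because entry is staggered. If looks are counted from first enrolment, anyone enrolled after day one is behind the calendar, so each look is made up of shorter follow-up from the earliest recruits. Section 4.2 justifies the 12-month intervention as the time needed to see meaningful change in quality of life, and Section 6.3 moves participants from individual to group sessions during months 6 to 12. An efficacy stop at calendar month 6 would rest on the first half of the programme only. If the choice of clock and visit is left until data are in hand, control of the type I error is no longer assured.

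**Working it through.** **Plan's own figure.** The table in Section 9.7 peaks at 102 participants. Allowing for 30% dropout, 102 / (1 − 0.30) = 145.7, rounded up to 146. This agrees with the plan. The plan gives no count of participants with data at each look, so that has to be derived.

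**Inputs.** Total of 146 (1.1, 9.7). Looks at L = 3, 6 and 12 months from first enrolment (9.6 with 4.4). Visits at 3, 6, 9 and 12 months (9.2), plus week 2 and week 48 (6.1). Assumptions, because the documents are silent: uniform accrual over A = 3, 6 or 12 months, and no dropout.

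**Formula.** Number with visit v at look L = 146 × min(1, max(0, (L − v)/A)). Week 2 is 14/30.4375 = 0.46 months. Week 48 is 336/30.4375 = 11.04 months.

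| Look and score | A = 3 | A = 6 | A = 12 |
|---|---|---|---|
| Month 3: any post-baseline score (week 2 or later) | 124 | 62 | 31 |
| Month 3: 3-month score | 0 | 0 | 0 |
| Month 6: 3-month score | 146 | 73 | 36 |
| Month 6: 6-month score | 0 | 0 | 0 |
| Month 12: 6-month score | 146 | 146 | 73 |
| Month 12: 9-month score | 146 | 73 | 36 |
| Month 12: week-48 score | 47 | 23 | 12 |
| Month 12: 12-month score | 0 | 0 | 0 |

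The entries of 36 are 36.5 rounded down. Example: the week-48 score at month 12 with A = 6 is 146 × (12 − 11.04)/6 = 23.4. The zeros follow from L − v = 0 and do not depend on A, provided entry is staggered. The only exception is a participant enrolled on day one.

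**What the open choice does to the boundary.** Take the month-6 look with A = 6, when 73 participants have a 3-month score (36.5 per arm). Use the 9.7 means of 70 and 85, and read the table's 20 as an SD. On that reading the z formula gives 22 per arm against the stated 21. Read as a variance, it would give 2 per arm. Suppose the full difference is already present at 3 months. Expected Z = 15 / (20 × √(2/36.5)) = 3.20.

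Cumulative one-sided spending at alpha 0.05 is 2 × [1 − Φ(1.96/√t)], where t is the information fraction:

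- t = 6/18 (calendar share): 0.0007 spent, boundary about 3.20, chance of crossing about 50%.
- t = 73/146 (participants with a 3-month score): 0.0056 spent, boundary about 2.54, chance of crossing about 75%.
- Information counted as 6-month or 12-month scores: t = 0, so there is no boundary.

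The same data could therefore meet a boundary of 3.20, a boundary of 2.54, or none, depending on a definition that the plan does not give. The alpha already spent at month 3 is negligible (0.0000016 at t = 3/18).

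**End of trial.** If Section 9 counts from first enrolment, the trial ends at month 18. Under 4.4 it ends at month 18 + A, that is 21, 24 or 30. If Section 9 means follow-up time, the two agree. This is a further reason to state the clock.

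**The case against.** A reader might infer that no scheduled look can hold 12-month FACT-G data, that the month-3 look is nearly empty, and that the trial could stop before anything is known about the full programme. The documents do not support that much.

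- A day-one enrollee does reach 12 months at the month-12 look.
- The biweekly schedule in 6.1 puts some post-baseline FACT-G data into the month-3 look. That look is near empty only for the 3-month or week-12 visit.
- The programme lasts 48 weeks, so the month-12 look contains end-of-programme scores for early recruits. Earlier visits also contribute to the planned MMRM.
- Twelve months is nowhere named as the primary visit, so it is not the plan's own standard for judging a look.
- The size depends on accrual. With accrual over 1 month, 140 of 146 would have the week-48 score at month 12. If everyone enrolled at once, calendar and follow-up time would coincide. The SAE window in 8.4 (15 April 2024 to 15 October 2025) is 18 months, which is compatible with a nearly simultaneous start, although 4.4 does not say so.
- Sections 1.3 and 9 can be read as follow-up time, and on that reading the 12-month look does contain 12-month data.

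Nor does calendar scheduling by itself rule out O'Brien-Fleming spending, because a spending function accepts looks at any time once the information fraction is known. Early boundaries are also strict.

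All of this stands, and it limits the point. It does not remove it. The follow-up reading does not override 9.6 but contradicts it, and neither reading comes with a visit or an information fraction.

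**Conclusion.** The concern holds as an inconsistency with a practical consequence. Sections 9.6 and 4.4 time the efficacy looks from first enrolment, while Sections 1.3 and 9 can be read as timing them by follow-up. Under the literal 9.6 rule and any staggered accrual, a month-v look has essentially no month-v FACT-G. That result needs no accrual figure. The counts of less mature data do need one: they rest on uniform accrual over an assumed 3, 6 or 12 months with no dropout, and they would be lower with the 30% dropout the plan expects. The crossing probabilities are illustrative and further assume an SD of 20 and the full effect at 3 months. The true information fractions cannot be derived from the documents. Because 9.6 permits an efficacy stop, this should be settled before any look is taken.

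**What to change.** In 9.6, name the FACT-G visit to which the efficacy boundary applies. Trigger each efficacy look by the number of participants with a FACT-G score at that visit. Compute the spending boundary at the resulting information fraction, and state the maximum number against which the fraction is taken (the plan offers 146 randomised and 102 expected to remain). Then make 1.3, 4.4, the opening of Section 9 and 9.6 agree on the clock for the looks and on the date of the final analysis. State the expected accrual period so that the calendar dates can be projected. If the combined protocol and SAP remains in use, carry the same changes into it for its own primary outcome.

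The cost is protocol and SAP wording, and efficacy looks that occur later. Calendar-based safety reviews are unaffected. Whether the month-3 and month-6 looks should be confined to safety is a matter of preference for the sponsor and is not required to resolve this point.

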9.7 Sample Size Determination

- The metric-wise sample size calculation is provided in the table below on alpha as 0.05 and power of 80% for the one-tail test at enrollment ratio = 1.
- While we are conducting the power analysis and sample size calculation based on several variables (outcomes) of interest, the sample size was computed separately for each parameter in the study and the greatest is used to obtain sample size.
- The analysis (detailed below in table) showed that sample of size of 102 is powerful enough for the analysis to cover 100% of primary and secondary metrics.
- Now since we believe that the long follow-up duration of 6 months for our trial will lead to around 30% drop-offs, we decided a final sample size of 146 (73 control, 73 test).

- So even if get 30% or 44 participants drop off we end up with final sample set of 102 (51 control, 51 test) and would be able to come to statistically significant effects ($p < 0.05$) with respect to 100% of primary and secondary metrics.

Metric Segment	Sub Metric	Control Data	Test Data	Assumed Variance	Sample Size
Primary Outcome / Concerns					
Quality of Life Improvement	QoLS Score (FACT-G)	70	85	Variance of 20	42 (21 Control, 21 Test)
Secondary Outcome / Concerns					
Presenteeism	Attitude towards work	2	4	Variance of 1.5	16 (8 Control, 8 Test)
	Employee Performance	0.6	0.7	Variance of 20%	102 (51 Control, 51 Test)
Absenteeism	Working Hours	30	40	Variance of 10	28 (14 Control, 14 Test)
	Vacation Days	0.5	0.3	Variance of 0.15	16 (8 Control, 8 Test)
Exploratory Outcomes					
Cancer Care	Cancer Progression Status	0.85	0.88	Variance of 0.04	46 (23 Control, 23 Test)

	Cancer recurrence status	0.3	0.21	Variance of 10%	32 (16 Control, 16 Test)
Medical Expenditure	Total Healthcare Expenditure (Planned + Unplanned)	10000	8000	Variance of 4000	102 (51 Control, 51 Test)
	No of Urgent Care Visits	3	2.5	Variance of 0.5	28 (14 Control, 14 Test)
	No of ED Visits	5	3.45	Variance of 0.8	10 (5 Control, 5 Test)
	No of unplanned outpatient/office visits (other than ED)	4.28	3.5	Variance of 0.8	28 (14 Control, 14 Test)
	Unplanned Hospitalisations	5	4	Variance of 0.8	18 (9 Control, 9 Test)
	Length of hospital stay	3	2	Variance of 0.8	18 (9 Control, 9 Test)
	No of planned outpatient visits	2	1.8	Variance of 0.3	58 (29 Control, 29 Test)
	No of planned hospital visits	1.25	1	Variance of 0.1	10 (5 Control, 5 Test)
	Length of hospital stay	3	2	Variance of 0.8	18 (9 Control, 9 Test)

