9.6 Interim Analyses

- Interim analyses are planned to evaluate the primary and secondary objectives' safety and efficacy data. These analyses may also explore data trends that could necessitate adjustments to the trial conduct.
- Statistical Methods:

- The interim analyses will employ group sequential testing methods with an O'Brien-Fleming spending function to rigorously control the type I error rate across multiple looks at the data.
- Execution:
 - The analyses will be performed by an independent biostatistician from the trial investigators to maintain objectivity.
- Timing and Triggers
 - Scheduled Interim Analyses: Interim analyses are planned at 3 months, 6 months and 12 months of trial commencement.
 - Ad Hoc Requests: Additional interim analyses may be conducted at the request of the Trial Monitoring Committee, particularly if unexpected safety concerns arise.
- Decision Criteria and Oversight
 - Decision Criteria: The criteria for early stopping or trial adaptation include a pre-specified boundary for efficacy (significant reduction in healthcare expenditure or improvement in health outcomes) or safety concerns (unacceptable adverse events rate).
 - The Trial Monitoring Committee will oversee the interim analyses, reviewing the results to make recommendations on continuing, stopping, or modifying the trial.
 - Blinding Integrity: Individuals analyzing the data may have access to unblinded data; however, measures will be taken to ensure that the trial team remains blinded to maintain the integrity of the trial implementation.
 - Authority to Stop or Modify: The ultimate authority to stop or modify the trial rests with the TMC, in consultation with the principal investigator and the sponsor, based on the interim findings and established stopping guidelines.

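### The interim efficacy criterion can be met by FACT-G or by undefined health outcomes, and no alpha is allocated across endpoints

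*Protocol*

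**What the plan says.** Protocol 9.6 opens by saying "Interim analyses are planned to evaluate the primary and secondary objectives' safety and efficacy data". It adopts group sequential testing with an "O'Brien-Fleming spending function to rigorously control the type I error rate across multiple looks at the data". The schedule is "Interim analyses are planned at 3 months, 6 months and 12 months of trial commencement", and the opening of Section 9 adds an analysis at 18 months, the end of the trial. Unscheduled looks are also possible: "Additional interim analyses may be conducted at the request of the Trial Monitoring Committee".

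Under Decision Criteria, the grounds for early stopping or adaptation include "a pre-specified boundary for efficacy (significant improvement in Quality of Life Scores or improvement in health outcomes". A separate safety ground follows. The section does not list the health outcomes, and the word *significant* is attached only to the quality-of-life limb.

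Section 9.6 of the Combined protocol and SAP has the same structure around its own primary endpoint: "significant reduction in healthcare expenditure or improvement in health outcomes".

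Neither document contains a testing hierarchy, a gatekeeping rule or an alpha split between endpoints. Protocol 9.7 sizes each metric separately at one-tailed 0.05 and expects p < 0.05 "with respect to 100% of primary and secondary metrics".

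**The concern.** A spending function distributes the error for one hypothesis over several looks. It does nothing about several hypotheses, any one of which can deliver the efficacy conclusion. The criterion in 9.6 joins two limbs with *or*, and leaves the second open.

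The trial could therefore stop, or be adapted, for efficacy on a non-primary outcome while FACT-G shows no difference. Because the outcomes are not named, the committee would in effect choose the qualifying one after seeing data. An early stop on that basis would also cut short collection of the primary endpoint.

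**Working it through.** **Inputs from the Protocol.** One-sided alpha 0.05 per metric (9.7); looks at 3, 6 and 12 months (9.6) and 18 months (opening of Section 9); O'Brien-Fleming spending (9.6). Endpoints in Section 3: FACT-G (primary), leave days, motivation and performance review (secondary).

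**Assumptions.** Information fractions 3/18, 6/18, 12/18 and 1, and correlation between endpoints from 0.8 to 0. The documents give neither. Unscheduled looks are not counted.

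**Step 1: the alpha each metric receives.** 9.6 gives no boundary values to reproduce, so I checked the sizing. The driving row is employee performance, 0.6 against 0.7, with the stated spread of 20% read as an SD of 0.2.

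n per arm = 2(1.645 + 0.842)²(0.2/0.1)² = 49.5, so 50, or 51 with the t distribution. The plan states 51. Then 102/0.7 = 145.7, so 146 as stated. A two-sided 0.05 would need 63 to 64 per arm. The figure therefore uses the full one-sided 0.05, with nothing reserved for other endpoints.

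**Step 2: one endpoint.** The O'Brien-Fleming-type function for one-sided 0.05 is α(t) = 2[1 − Φ(1.96/√t)].
- α(12/18) = 2[1 − Φ(2.40)] = 0.0164
- α(1) = 0.05

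The z boundaries are about 4.66, 3.21, 2.15 and 1.70. For FACT-G alone the total is 5.0%, of which 1.6% is spent by 12 months.

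**Step 3: several endpoints, closed form at zero correlation.**
- Any crossing by 12 months: 1 − 0.9836² = 0.0325 (two); 1 − 0.9836⁴ = 0.0640 (four).
- Any endpoint can stop early, only FACT-G counts at the end: 1 − 0.95 × 0.9836 = 0.0656 (two); 1 − 0.95 × 0.9836³ = 0.0960 (four).
- Any endpoint at every look: 1 − 0.95² = 0.0975 (two); 1 − 0.95⁴ = 0.1855 (four).

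**Step 4: correlation 0.8 to 0, by simulation with every true effect zero.**

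| Endpoints that can cross | False crossing by 12 months | Any early, FACT-G only at end | Any endpoint, every look |
|---|---|---|---|
| 1 (FACT-G) | 1.6% | 5.0% | 5.0% |
| 2 | 2.6–3.2% | 5.7–6.5% | 7.6–9.7% |
| 4 | 3.9–6.3% | 6.7–9.5% | 10.7–18.5% |

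The upper ends agree with Step 3 to about 0.1 percentage point.

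**Step 5: sensitivity to the fractions.** With equal spacing (0.25, 0.5, 0.75, 1), the crossing probability by the third look is 2.4% for one endpoint, 3.7–4.7% for two and 5.5–9.1% for four. The last column barely moves. The early-stop figures depend on the fractions; the all-looks totals hardly do.

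**Where the counts come from.** Two is FACT-G plus one health outcome, which is the least that the *or* clause allows. Four is every primary and secondary endpoint. That count rests on the opening sentence of 9.6, not on the *or* clause, because the endpoint rationale in 4.2 distinguishes work-related outcomes from health parameters.

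**The case against.** The strongest reply is that 9.6 promises error control across looks and nothing more. That stands. A reader might infer that the statement on type I error is false. For FACT-G alone at the scheduled looks it can be true; what is missing is any treatment of multiplicity across endpoints.

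Second, *health outcomes* may partly restate quality of life, since 2.1 counts quality of life among them. This only partly helps. 2.1 treats quality of life as one member of a wider class, and 9.1 sets cancer progression beside quality of life in describing the primary analysis. The list stays open.

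Third, a reader might infer that any favourable direction on a health outcome would suffice, so that the limb is met half the time by chance. The text does not support that. The words explain a pre-specified boundary under a group sequential method, a boundary implies a threshold, and *significant* can be read as governing both limbs. What remains is an ambiguity.

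Fourth, a reader might widen the family to the exploratory outcomes, or take 18.5% as the chance of a wrongful early stop. The opening sentence of 9.6 names only primary and secondary objectives, and 18.5% includes crossings at the final analysis. The 9.7 expectation of significance on every metric is a statement about power, not an interim rule, so it is only background here.

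**Conclusion.** The point holds in this form: the efficacy criterion is disjunctive, its second limb is undefined, and no alpha is allocated across endpoints. O'Brien-Fleming spending can protect FACT-G but not the trial-level efficacy conclusion.

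The early-stopping effect is moderate, from 1.6% to between 2.6% and 6.3% by 12 months. The total exceeds 5% in every scenario computed with two or more endpoints and no alpha split, from 5.7% up to 18.5% depending on what counts at the end.

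These figures assume a full one-sided 5% boundary on each endpoint, together with the fractions and correlations stated above. They apply to the Protocol. The Combined document has the same flaw but lists more secondary endpoints, so four is not its count.

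**What to change.** In Protocol 9.6, delete the health-outcomes limb. State that the efficacy boundary applies only to the between-group difference in FACT-G change at one named time point. The time point is essential: 9.2 tests at several and singles out none, so multiplicity within FACT-G would otherwise remain. State the information fraction at each look for that contrast, since a look taken before participants reach the time point holds no data on it.

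Say that secondary and exploratory outcomes are summarised for the committee at interims but cannot trigger an efficacy stop. Leave the safety criterion unchanged.

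For the final analysis, either give a multiplicity rule for the secondary endpoints, for example a fixed order after FACT-G, or label them as not error-controlled.

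In 9.6 of the Combined document, attach the boundary only to total healthcare expenditure.

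If the sponsor wants to keep two limbs, the second must be one defined endpoint and alpha must be split. At 0.025 each, the total is 4.9% at correlation 0 and 3.9% at 0.8.

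The preferred change costs wording only. Its downside is that a striking secondary result could not stop the trial for efficacy.
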